	•	12 - Employment History	
•	•	13 - Adverse Effects Form	
•	•	14 - Daily SMS Survey	
-	-	15 - USPHS Quit Smoking Handout (modified)	

Appendix 16 - SMS Observation Survey (after enrollment - prior to V2)	66
Appendix 17 - Participant Instructions for Hydroxyzine	67
Appendix 18 - Participant Instructions for Varenicline	68
Appendix 19 - 6-Month Follow Up Survey	69
Annendix 20 - Modified Cigarette Evaluation Questionnaire (mCEO)	70

LIST OF ABBREVIATIONS

AE	Adverse event	
ALT	Alanine aminotransferase	
AP	Alkaline phosphatase	
ASP	Application Service Provider	
AST	Aspartate aminotransferase	
BUN	Blood urea nitrogen	
СС	Conventional cigarette	
CDC	Center for Disease Control and Prevention	
CFR	Code of Federal Regulations	
CO	Carbon monoxide	
CRF	Case report form	
CRM	Customer relationship management	
ECG	Electrocardiogram	
EOS End of Study		
FDA	Food and Drug Administration	
FTND	Fagerström test for nicotine dependence	
GCP	Good Clinical Practice	
HCG	Human chorionic gonadotropin	
ICF	Informed consent form	

ICH International Conference on Harmonisation

IRB Institutional Review Board

Kg Kilograms

Lbs pounds

QTc Corrected QT interval

mCEQ Modified Cigarette Evaluation Questionnaire.

MCH Mean corpuscular hemoglobin

MCHC Mean corpuscular hemoglobin concentration

MCV Mean corpuscular volume

Mg Milligram

mL Milliliter

nAChR Nicotinic Acetylcholine Receptor

MNWS Minnesota Nicotine Withdrawal Scale

PHQ-9 The Patient Health Questionnaire

PPM Parts per million

RBC Red blood cell (count)

RCT Randomized Control Trial

RRC Rose Research Center, LLC.

SaaS Software-as-a-Service

SAE Serious adverse event

SMS Short Message Service

SOP Standard operating procedure

SSL Secure Sockets Layer

STAI State-Trait Anxiety Inventory

TLS Transport Layer Security

V Voltage

W Wattage

WBC White blood cell (count)

WHO World Health Organization

WI-PREPARE The Wisconsin Predicting Patients' Relapse Questionnaire

1 Introduction

1.1 STUDY DESIGN AND PLAN

This open-label study will evaluate hydroxyzine, a first-generation antihistamine, combined with varenicline, to help smokers abstain from smoking during a 12-week trial period by diminishing the nausea, stress, anxiety, and sleep disturbances associated with the use of varenicline and with nicotine withdrawal.

1.2 BACKGROUND

Cigarette smoking remains the leading cause of preventable death in the U.S., and is one of the leading causes of preventable morbidity and mortality. An estimated 540,000 smokers die each year from smoking-related diseases. Existing treatments for tobacco cessation yield, on average, less than 25% long-term abstinence rates, with many of the cessation failures occurring within the first month of abstinence. There is an urgent need to develop new therapies for smoking cessation, including repurposing FDA-approved medications. Current pharmacological approaches (e.g. nicotine replacement therapy, bupropion, or varenicline) increase efficacy for smoking cessation, but continue to have poor long-term abstinence rates, with potentially concerning adverse events.

Research into the predictors of smoking lapse, the initial step in smoking relapse and unsuccessful quit attempts, demonstrate the importance of stress as it relates to smoking cessation. In 2011, McKee, et. al. demonstrated that stress decreases the ability to resist smoking. An individual's response to stress from the discomfort of nicotine withdrawal and quitting smoking (so called "distress tolerance") may be an important factor in successful and persistent abstinence from smoking. Additionally, sleep disturbances during smoking cessation, either as a withdrawal symptom from nicotine, or as a side effect of treatment medications (like varenicline), may play an important role in failed smoking cessation attempts. One of the most successful medications, varenicline, a full agonist on α 7-nicotinic acetylcholine receptors (nAChRs) and a partial agonist on the α 4 β 2, α 3 β 4, and α 6 β 2 subtypes, has side effects which include nausea, difficulty sleeping, and nightmares. One of the most successful medications (like varenicline) are the α 4 β 2 subtypes, has side effects which include nausea, difficulty sleeping, and nightmares.

Hydroxyzine is an FDA approved first-generation antihistamine of the diphenylmethane and piperazine class that has antiemetic, anxiolytic, and sedative effects. Hydroxyzine's effects are primarily derived due to its actions as a potent H1 receptor inverse agonist. It also acts as an antagonist on the 5-HT2A, D2, and α 1-adrenergic receptors. Because of its antiserotonergic effects, as well as the antagonistic effects on multiple receptor systems in the brain, hydroxyzine is noted to have strong anxiolytic properties, as well as mild antiobsessive and antipsychotic properties. Even with its effective sedative, hypnotic, and anxiolytic effects, hydroxyzine does not demonstrate any of the abuse, dependence, addiction or toxicity potential associated with medications within the same therapeutic range (such as benzodiazepines or nonbenzodiazepine hypnotics). 13

In vitro studies point to the important role of H1 receptor antagonist (antihistamines) on the functional properties of cloned $\alpha 7$ - nicotine acetylcholine receptor expressed in *Xenopus* oocytes. ¹⁴ Recent clinical trials have investigated antihistamines as potential aids in quitting smoking. This includes animal models which

evaluated the effects of the antihistamine pyrilamine (a centrally acting first-generation antihistamine) on Sprague-Dawley rats self-administering nicotine. This study showed significant reductions in nicotine self-administration with both acute dosing and repeated injections of this centrally acting antihistamine. ^{15(p1)} A recent study at Duke University evaluated meclizine (a first-generation nonselective H1 antagonist) as a potential smoking cessation treatment. In this phase II study completed in 2013, participants were given a divided dose of meclizine (either 25 mg a day or 50 mg a day, administered in two doses each day) with a nicotine patch for three weeks during the pre-quit period. The study results demonstrate the high potential for this class of medications to provide improved rates of abstinence for smokers who desire to quit. ¹⁶ As opposed to hydroxyzine, meclizine is not recognized to have anxiolytic properties, and has a much shorter half-live, only six hours, compared to hydroxyzine which has a half-life of about 20 hours. ^{17,18}

This study investigates the potential for decreasing the rate of adverse effects of varenicline and increasing the efficacy of varenicline when it is combined with hydroxyzine. Since hydroxyzine is an FDA-approved medication, marketed in the United States, it does not require an IND (Investigational New Drug) application. This study is not intended to support a new indication, support a change in labeling, support a change in advertising, nor does it involve a change in dosage level or route of administration.

2 STUDY OBJECTIVES AND ENDPOINTS

2.1 EFFICACY OF VARENICLINE AND HYDROXYZINE FOR STRESS AND SLEEP

A maximum of fifty (50) smokers will receive the FDA-approved dosing for both varenicline and hydroxyzine. These medications have been approved by the FDA for use by healthy, non-pregnant adults at the doses and frequencies specified in this study.

Participants enrolled in the study will take the FDA approved starter kit of varenicline for the first week of medication administration (0.5 mg nightly for days 1-3, then 0.5 mg twice daily for days 4-7). During the first week, participants will also receive hydroxyzine dosed in a similar manner, 50 mg nightly for the first 3 days, then twice daily, 25 mg in the morning and 50 mg at night. After the first week, participants will receive the FDA-approved dose of varenicline (1 mg twice daily) combined with hydroxyzine, 25 mg in the morning and 50 mg at nighttime. All medications will be dosed orally. The FDA has approved the 50 mg dose of hydroxyzine for treatment of nausea, anxiety, and insomnia. The morning dose of hydroxyzine is limited to 25 mg to minimize the sedative effects of this antihistamine, while the evening dose is prescribed at 50 mg to maximize the antiemetic, anxiolytic, and sedative properties. Dose adjustments for hydroxyzine by licensed medical providers may occur based on adverse effects reported by participants (e.g. daytime sedation...stop the AM dose of hydroxyzine, difficulty waking in the am...decrease nighttime dose of hydroxyzine). Participants will be contacted with a follow-up call by Research Medical Staff within 72 hours of any dose adjustment. Trial medications will continue until the participant returns for the End-of-Study visit, approximately 12 weeks after initiation of the medications.

2.1.1 Stress

Stress levels will be measured using the 10-item Perceived Stress Scale (PSS-10) at each laboratory session.

2.1.2 Anxiety and Depression

Anxiety levels and depression will be monitored using the 6-item State-Trait Anxiety Inventory (STAI) and the Patient Health Questionnaire (PHQ-9) provided during each laboratory sessions.

2.1.3 Additional Monitoring

Participants will respond to the Fagerström Test for Nicotine Dependence (FTND) and the Minnesota Nicotine Withdrawal Scale at each laboratory session after enrollment. Participants will also respond to the Modified Cigarette Evaluation Questionnaire (mCEQ, satisfaction with smoking) and the "Wisconsin Predicting Patients' Relapse" questionnaire (WI-PREPARE, susceptibility to smoking relapse) at Visit 2 and Visit 3. Spontaneous reduction in *ad libitum* smoking will be monitored with daily cigarette-use diaries, via SMS text messages. Data collection will begin upon enrollment and continuing until the End-Of-Study visit.

2.1.4 Side Effects and Tolerability data

Tolerability will be evaluated using open-ended as well as targeted side effect assessments at each visit. Participants will be queried on their level of nausea via daily SMS text messages.

2.2 EFFECTS OF VARENICLINE ON SMOKING REDUCTION PRIOR TO THE QUIT DATE

Previous research has shown that abstinence at the end of treatment is strongly predicted by the extent to which smokers spontaneously reduce *ad libitum* smoking in the initial weeks of pharmacotherapy that is initiated before the quit-smoking date. This finding was initially discovered by the principal investigator (2009) using pre-quit date nicotine skin patch treatment and has been extended by other investigators who have found similar results using bupropion and varenicline. This early marker of subsequent success can be extremely useful in clinical practice by helping to guide adaptive changes in treatment before a potential relapse occurs. We will assess the extent of smoking reduction in participants during the initial seven days of treatment (prior to their planned quit date) through the End-Of-Study, indexed by smoking diaries and biochemical measures (expired air carbon monoxide). We will correlate these reductions with abstinence assessed at the end of treatment.

2.3 Identify Additional Early Predictors of Treatment Outcome

In addition to pre-quit reductions in ad libitum smoking, several other variables will be assessed in the first week before the quit-smoking date and correlated with end-of-treatment abstinence. These measures include: a) subjective ratings of the rewarding effects of smoking, craving for cigarettes and other nicotine withdrawal symptoms, assessed using standardized questionnaires; b) demographic measures, including gender, age, socioeconomic status, and race; and c) smoking history variables, including baseline cigarette consumption, level of nicotine dependence, and number of prior quit attempts.

2.3.1 Self-report of Smoking Behaviors and Nicotine dependence

Number of cigarettes smoked per day will be evaluated using daily diaries. Nicotine dependence measures will be taken using the Fagerström Test for Nicotine Dependence (FTND).²²

2.3.2 Self-reported Rewarding / Aversive Effects of Cigarettes

Rewarding and aversive effects will be evaluated using the validated modified Cigarette Evaluation Questionnaire (mCEQ)²³, initially developed in the Principal Investigator's laboratory. The mCEQ assesses the degree to which participants experience the reinforcing effects of smoking, providing five subscale scores: smoking satisfaction (satisfying, tastes good, enjoy smoking), psychological reward (calms down, more awake, less irritable, helps concentrate, reduces hunger), aversion (dizziness, nauseated), enjoyment of respiratory tract sensations (single-item assessment), and craving reduction (single-item assessment).

3 Investigational Plan

3.1 STUDY DESIGN

This study design has been developed to hasten the identification and evaluation of promising new smoking cessation treatments. This single-group, small-scale, open-label study (N= maximum of 50) will evaluate hydroxyzine combined with varenicline. The rate of nausea reported in this study will be compared to the known nausea rates associated with varenicline alone (~30%). Interim data analysis will occur after 25 participants have reached the primary outcome. In choosing these thresholds, Monte Carlo simulations were conducted to determine the significance thresholds for both the N=25 and N=50 one-tailed binomial tests so that the overall false positive (Type I error) rate across all tests would be approximately 10%. Conversely, the overall false negative (Type II error) rate, whereby a promising treatment is discarded prematurely, would be approximately 20%. These initial results will fall into one of three categories:

3.1.1 Reported nausea 12% or less of participants

If three or less participants report nausea with combination hydroxyzine and varenicline, this investigational treatment will be viewed as having considerable promise and will immediately be advanced to a larger-scale (~N=200) randomized controlled clinical trial (RCT) and this "pilot" study will stop recruitment. This RCT will be submitted as a separate protocol.

[figure not shown]
3.1.2 Reported nausea in 16% to 24% of participants

If 4 to 6 participants report nausea with combination hydroxyzine and varenicline, an additional 25 participants will be recruited to obtain a more precise estimate of the success rate. If, cumulatively, reported nausea is less than 20% (10/50), the combination of hydroxyzine and varenicline will be advanced to a larger-scale (~N=200) RCT.

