13.1.2 Side Effects / Tolerability

The hypothesis that hydroxyzine reduces the incidence of nausea, one of the most common side effects of varenicline, will be evaluated by comparison to the benchmark of 30% (20% above placebo rate of 10%) observed in clinical trials of varenicline.³⁶ Initially, 25 participants will be recruited and then the possibility of recruiting 25 more (total N=50) depending on an interim analysis, as follows:

- If 0-3 participants out of 25 (12% or less) report nausea, we would conclude the treatment is highly promising at the interim stage and go directly to an RCT (Branch 1).
- If 4-6 participants (out of 25) report the side effect, then the treatment will be deemed sufficiently promising to recruit an additional 25 participants (Branch 2). If 10 or less of the total 50 report the side effect of nausea (20% or less), a follow-up RCT would be warranted; otherwise the treatment would be deemed unpromising.
- If 7 or more out of 25 (28% or more) report the side effect of nausea in the interim analysis, then we would conclude it is futile to continue the pilot and the study would be terminated (Branch 3).

The frequency of treatment-emergent side effects (i.e., those that begin or worsen after the initiation of treatment) will be tabulated. Due to the problem of Type II error posed by significance testing numerous side effect outcomes (especially if corrections are imposed for multiple comparisons), descriptive statistical methods will instead be used, supplemented by calculation of confidence intervals and p-values as a flagging device to highlight differences worthy of further attention.³⁷ Hypothesis testing will be conducted for only two outcomes: 1) proportion of participants that withdraw from the study due to side effects; 2) overall adherence (i.e., proportion of scheduled doses taken) assessed by daily medication diaries and returned capsules.

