13.1.3 Statistical Power

Monte Carlo simulations conducted by our statistical consultant ([name]) revealed that if the combination hydroxyzine/varenicline treatment is no better than varenicline alone (null of 30% incidence of nausea is true) the following would occur:

- 3% go into Branch 1 (highly promising)
- 31% go into Branch 2 (larger pilot)

- 66% go into Branch 3 (early evidence of futility)
- Overall Type I error rate of 9%

If the new treatment yields a side effect rate of 15% (versus null of 30%) then:

- 47% go into Branch 1 (highly promising)
- 46% go into Branch 2 (larger pilot)
- 7% go into Branch 3 (futile)
- Overall power of 86%

If the new treatment yields a side effect rate no worse than placebo of 10% (versus null of 30%) then:

- 77% go into Branch 1 (highly promising)
- 22% go into Branch 2 (larger pilot)
- 1% go into Branch 3 (futile)
- Overall power of 98%

Thus, to detect a clinically important reduction in side effects (a relative reduction by at least 50%, from an incidence of 30% to 15% or less), the power exceeds 86%. The Type I error of the overall approach is 9%.

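### Section 3.1.2 and Section 13.1.2 set different final go/no-go cut-offs: exactly 10 of 50 with nausea fails one and passes the other, and the stated 9% Type I error and 86% power fit only the second

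*Combined protocol and SAP*

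**What the plan says.** The design has two stages. Sections 3.1.1 to 3.1.3 and Section 13.1.2 agree on the interim look at 25 participants:

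- Branch 1, go straight to an RCT: "If 0-3 participants out of 25 (12% or less) report nausea".
- Branch 2, recruit 25 more: "If 4-6 participants (out of 25) report the side effect".
- Branch 3, stop for futility: "If 7 or more out of 25 (28% or more) report the side effect of nausea in the interim analysis".

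They disagree on the final decision at 50 participants:

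- Section 3.1.2: "If, cumulatively, reported nausea is less than 20% (10/50), the combination of hydroxyzine and varenicline will be advanced to a larger-scale" RCT.
- Section 13.1.2: "If 10 or less of the total 50 report the side effect of nausea (20% or less), a follow-up RCT would be warranted". Any other result is classed as unpromising.

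Section 13.1.3 gives one set of operating characteristics and does not restate the final cut-off. Overall Type I error is 9% when the "null of 30% incidence of nausea is true", power is 86% at 15% nausea, and power is 98% at 10% nausea. It sums up the power for a reduction "from an incidence of 30% to 15% or less), the power exceeds 86" percent. Section 3.1 gives design targets: a Type I error of about 10%, and "the overall false negative (Type II error) rate, whereby a promising treatment is discarded prematurely, would be approximately 20" percent. It does not name the nausea rate to which the Type II figure applies.

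**The concern.** Ten of 50 is exactly 20%. Section 3.1.2 requires a rate strictly below 20%, so 10/50 does not advance. Section 13.1.2 includes 20%, so 10/50 does advance.

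Reduced nausea is the main hypothesis (Section 13.1.1), and this cut-off is its final decision rule, leading to an RCT of about 200 participants. The study is open-label with a single group. If 10/50 occurred, someone would choose between two written rules with the result in view, and either choice could be defended from the protocol. Until one rule is fixed, it is also unclear which design the stated error rates describe.

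**Working it through.** **Inputs.** Interim bands 0–3, 4–6 and 7 or more of 25, and the final cut-off c = 10, from Section 13.1.2. The alternative c = 9 is the largest count below 20% of 50 (Section 3.1.2). Nausea rates p = 0.30, 0.15 and 0.10 from Section 13.1.3.

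**Formula.** With X1 and X2 independent Binomial(25, p) counts for the two stages,

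P(advance) = P(X1 ≤ 3) + Σ over x = 4, 5, 6 of P(X1 = x) · P(X2 ≤ c − x).

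**Step 1: branch probabilities.** These do not depend on c, so they test the model alone.

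| True rate | Branch 1 / 2 / 3, exact | Branch 1 / 2 / 3, Section 13.1.3 |
|---|---|---|
| 30% | 3.3 / 30.7 / 65.9% | 3 / 31 / 66% |
| 15% | 47.1 / 45.9 / 7.0% | 47 / 46 / 7% |
| 10% | 76.4 / 22.7 / 1.0% | 77 / 22 / 1% |

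All agree within one point, as expected when exact values are set beside Monte Carlo results.

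**Step 2: numbers put in.** Terms are rounded to four decimals.

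- p = 0.15, c = 10: 0.4711 + 0.2110·0.9305 + 0.1564·0.8385 + 0.0920·0.6821 = 0.861.
- p = 0.15, c = 9: 0.4711 + 0.2110·0.8385 + 0.1564·0.6821 + 0.0920·0.4711 = 0.798.
- p = 0.30, c = 10: 0.0332 + 0.0572·0.3407 + 0.1030·0.1935 + 0.1472·0.0905 = 0.086.
- p = 0.30, c = 9: 0.0332 + 0.0572·0.1935 + 0.1030·0.0905 + 0.1472·0.0332 = 0.0585.

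**Step 3: comparison with the stated figures.**

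| Quantity | Section 13.1.3 | 10 or fewer of 50 | 9 or fewer of 50 |
|---|---|---|---|
| Type I error, p = 30% | 9% | 8.6% | 5.9% |
| Power, p = 15% | 86% | 86.1% | 79.8% |
| Power, p = 10% | 98% | 98.5% | 97.4% |

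The first two rows fit only the inclusive rule. The third is close under both and does not separate them. Ignoring the interim look does not rescue the strict rule: a single-stage test at N = 50 gives 7.9% and 88.0% with 10 or fewer, and 4.0% and 79.1% with 9 or fewer. Neither pair matches 9% and 86%.

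**Step 4: chance of the disputed result.** The probability of entering Branch 2 and ending on exactly 10 is Σ over x = 4, 5, 6 of P(X1 = x) · P(X2 = 10 − x).

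| True rate | Exactly 10/50 | As a share of trials entering Branch 2 |
|---|---|---|
| 10% | 1.1% | 4.8% |
| 15% | 6.3% | 13.8% |
| 20% (not a protocol scenario) | 9.9% | 18.2% |
| 30% | 2.8% | 8.9% |

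**Step 5: the Section 3.1 targets.** Assume the unnamed alternative is 15%, the rate that Section 13.1.3 treats as the clinically important reduction. Type II error is then 100 − 86.1 = 13.9% under the inclusive rule and 100 − 79.8 = 20.2% under the strict rule. The Type II target of about 20% matches the strict rule, while the Type I target of about 10% is nearer the inclusive rule (8.6% against 5.9%). Section 3.1 therefore does not settle which cut-off was meant.

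**The case against.** The strongest reply is that this is loose drafting with an obvious resolution. Section 13.1.2 is the statistical section, and its rule is complete: a count, a percentage and the consequence otherwise. The Type I error and the power at 15% in Section 13.1.3 fit that rule, and the parenthesis in Section 3.1.2 itself names 10/50. Only one outcome is affected, the interim rules agree throughout, and the RCT would need its own protocol. The Section 3.1 figures could be rounded targets, with Section 13.1.3 giving what was achieved. On that reading, 14% against a target of about 20% is not an error.

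Much of this is fair. The inclusive rule is probably the one that was simulated. The match between the strict rule and the 20% Type II figure depends on assuming a 15% alternative. Across the protocol's own three scenarios, the chance of exactly 10/50 is modest, at 1.1% to 6.3%.

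The contradiction remains. The wording of Section 3.1.2 excludes 20%, and no clause gives Section 13 precedence. A go/no-go rule should not have to be recovered by rerunning its simulation. The stepwise diagram for Section 3.1.4 was not available for this review, so it could not be checked for a cut-off of its own.

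**Conclusion.** The point holds: the final decision rule is wrong as written, because two current sections give opposite decisions at exactly 10/50. Relative to the inclusive rule, the strict rule lowers Type I error by 8.60 − 5.85 = 2.75 points and power at 15% nausea by 86.1 − 79.8 = 6.3 points. The stated 9% and 86% therefore describe the 10-or-fewer rule and not the 9-or-fewer rule.

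The calculation assumes independent participants with a common nausea rate and 25 evaluable participants per stage. Agreement with the published branch probabilities supports that model. The statement that Section 3.1's Type II figure should read about 14% also needs the 15% alternative, which Section 3.1 does not name. The conflict between the two cut-offs needs no assumption. It should be corrected because it concerns the study's main decision threshold and costs almost nothing to put right.

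**What to change.** Use one cut-off in both sections, fixed before the data are seen.

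**Simplest option.** Change Section 3.1.2 to 10 or fewer of 50 (20% or less), the rule behind Section 13.1.3. In Section 3.1, change the Type II error to about 14% and name the 15% alternative, or label 20% explicitly as an upper design target. This costs one sentence and one figure.

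**If strictly below 20% is intended.** Change Section 13.1.2 to 9 or fewer of 50. Restate Section 13.1.3 as about 6% Type I error, 80% power at 15% and 97% power at 10%, and revise the Type I target of about 10% in Section 3.1. This touches more text and gives up about 6 points of power at 15%.

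Under either option, check that the Section 3.1.4 diagram shows the same cut-off. Neither option adds participants or procedures.
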